4.2. PER PROTOCOL (PP) POPULATION

All subjects in the FAS population who complete the 4-week Treatment Period or discontinue from study treatment due to adverse event(s) or lack of efficacy, with the exception of major protocol violators. If a diary compliance is < 70% or treatment compliance is < 80% then the subject is excluded from the PP Population. Subjects with Week 4 visit outside of the window 28 +/- 3 (study days 25 to 31) days will be excluded from the PP Population. Final decisions regarding exclusion from the PP Population will be made prior to unblinding the database.

4.3. SAFETY POPULATION

All randomized subjects who receive at least one dose of the study drug. Subjects will be analyzed according to the treatment received. All safety analyses will be based on the Safety Population.

4.4. INTENSIVE PK POPULATION

Approximately 70 subjects who enrolled for the intensive PK sampling (30, 60, 90, and 120 minutes post-dose on Day 1) at the selected cities.

5. STATISTICAL METHODS

Seven treatment groups are identified for all analyses cited in the following as “by treatment group”: subjects in Age Group A receiving plecanatide doses of 0.5 mg, 1.0 mg, or placebo; subjects in Age Group B receiving plecanatide doses of 1.0 mg, 2.0 mg, 3.0 mg, or placebo. Following comparisons will be included:

1) For Age Group A:

Age: 6 to 11 years				
0.5 mg	1.0 mg	Active Doses Combined	Placebo	

2) For Age Group B:

Age: 12 to < 18 years				
1.0 mg	2.0 mg	3.0 mg	Active Doses Combined	Placebo

3) Overall:

Overall	
Plecanatide	Placebo

Descriptive statistical methods will be used to summarize the data from this study, with hypothesis testing performed for the primary and secondary efficacy endpoints. Unless stated otherwise, the term “descriptive statistics” refers to number of subjects (n), mean, median, standard deviation (SD), minimum and maximum for continuous data and frequencies and percentages for categorical data. Unless otherwise

noted, percentages will be calculated using the total number of subjects in the appropriate population and/or subgroup and per treatment group where applicable. Where data are collected over time, both the observed data and change from the Screening Period (baseline) will be summarized at each time point.

Statistical testing including p-values and confidence intervals (CIs) will be presented as described in each section below. The Type I error rate (alpha) for the analysis of the primary efficacy endpoint is 0.05 (two-sided).

Where applicable, comparisons among treatment groups will be performed using an analysis of variance/covariance (ANOVA/ANCOVA) model for continuous variables and a Cochran-Mantel-Haenszel (CMH) test for categorical variables.

For all repeated measures efficacy analyses, the following covariance structures will be examined: compound symmetry, first order autoregressive, and unstructured. The covariance structure with the best model fit will be selected for each efficacy endpoint.

All data collected during the study will be included in data listings. Unless otherwise noted, the data will be sorted first by treatment group, subject number, and then by date within each subject number.

The statistical analyses will be conducted with the SAS® System version 9.4 or higher. All analyses will be subject to formal verification procedures. Specifically, results will be verified utilizing independent programming prior to issuance of the draft statistical report. All documents will be verified by the lead statistician to ensure accuracy and consistency of analyses.

5.1. SUBJECT DISPOSITION, DEMOGRAPHICS, EXPOSURE AND DEVIATIONS

5.1.1. Subject Disposition, Demographics and Baseline Characteristics

Subject disposition will be presented for all enrolled subjects. The number of screened subjects, screen failures, reason for screen failures, and randomized subjects will be presented by study population and treatment group. The number of subjects who completed the study and discontinued from the study will be provided. The primary reasons for discontinuation at any point also will be presented by treatment group. The reasons for discontinuation of study participation at any time point will also will be presented by treatment group. Additionally, days on study will be summarized by treatment group.

Demographic data and baseline characteristics including age at screening, race, ethnicity, gender, height, weight, and BMI at screening will be summarized using descriptive statistics for each population.

Comparisons among treatment groups will be performed using an analysis of variance (ANOVA) model for continuous variables and a Cochran-Mantel-Haenszel (CMH) test for categorical variables.

A listing and descriptive summary of standard 12-lead ECG at screening will be provided. Also, a listing of medical history will be provided.

Additionally, a separate listing of discontinuation due to COVID-19 disruption will be provided.

5.1.2. Protocol Deviations

Deviations from the study protocol, including violations of inclusion/exclusion criteria, will be assessed as “minor” or “major”. A listing of protocol deviations and major protocol deviation will be provided. Additionally, a separate listing of inclusion criteria not met and exclusion criteria that were met will be provided.

5.1.3. Exposure and Compliance

Dosing compliance will be defined by the dosing compliance ratio: the number of doses actually taken by the subject divided by the number of doses that were expected to be taken during the same period multiplied by 100. Treatment compliance is defined as taking equal to or greater than 80% of the drug dosage prescribed. Otherwise, the subject will be considered noncompliant with study treatment. Rates of treatment compliance (<80%, ≥80%) as defined above will be compared between treatment groups using the Cochran–Mantel–Haenszel. A listing of study drug accountability will be provided.

5.2. EFFICACY ANALYSIS

5.2.1. Primary Efficacy Endpoint

The primary efficacy endpoint is the change from baseline in weekly SBM frequency over the 4 Week Treatment Period compared to placebo across treatment groups.

5.2.2. Primary Efficacy Analysis

The weekly SBM rate for each subject will be computed for each week of the 4-week treatment period. The change from baseline in mean weekly SBM rate will be analyzed using a linear mixed-effects model with fixed effects for gender (stratification variable), treatment, week, the interaction of treatment and week, and the corresponding baseline value; a random intercept for subject will also be specified. The least squares (LS) mean change from baseline will be presented, by treatment groups, and the difference in LS means for each treatment group versus placebo and combined active doses within each age group versus placebo in a separate model for each age group, and overall active doses versus placebo in a separate model with 95% confidence intervals and corresponding statistical p-values.

The baseline SBM weekly rate will be the weekly average number of SBMs recorded during each of the 2 weeks preceding initiation of study drug.

The above analysis will be repeated for the PP Population.

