8.8.2.4 Change from Baseline in Stool Consistency (mBSFS-C or BSFS)

Stool consistency for a bowel movement is measured using the mBSFS-C for patients in Group A and the BSFS for patients in Group B. The weekly average stool consistency scores will be determined using the approach defined in **Section 8.4.1** and presented for each week in the 4-week treatment period; the baseline weekly average is determined as described in **Section 8.4.3**. The change from baseline in the average weekly stool consistency score will be analyzed in the FAS Population using a linear mixed-effects model with fixed effects for gender (stratification variable), treatment, week, the interaction of treatment and week, and the corresponding baseline value, and a random intercept for patient. Least Squares (LS) means, with 95% confidence intervals and the corresponding statistical p-value, will be presented for each week, and across all 4 weeks, of the 4-week treatment period for the difference between the difference in LS means for each of treatment groups A and B versus Placebo. The analysis of interest for this secondary endpoint is the difference in LS means between each plecanatide group and placebo for the estimated overall average change from baseline across the 4-week treatment period.

The above analysis will be repeated for the PP Population.

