The Sponsor, Medical Monitor, or designated Safety Representative will request permission to follow the patient's progress with the doctor medically responsible for the pregnancy. If additional information on the progress of the pregnancy and/or any maternal AE is received "spontaneously" by the clinical site, the Investigator (or authorized delegate) should submit a follow-up Pregnancy Report Form to the Sponsor within 24 hours of becoming aware of the information.

[figure not shown]
If additional information on the outcome of the pregnancy and/or the details of the birth/delivery is received "spontaneously" by the clinical site, the Investigator (or authorized delegate) should also submit a pregnancy outcome report form to the designated Safety Contact within 24 hours of becoming aware of the information. If the outcome of the pregnancy is reported as premature birth, or as elective termination due to a medical reason or as spontaneous or accidental miscarriage, the details of the outcome should be described in the narrative section of the outcome Pregnancy Report Form. The pregnancy outcome will generally be reported as a follow-up report. Details of birth/delivery, including date of birth, weight, and sex of the fetus/newborn should also be described in the narrative field of the Pregnancy Report Form.

Complete a new SAE Report Form if the delivery outcome meets the criteria for a SAE (e.g., congenital anomaly/birth defect, still birth, some other sickness, etc.). The SAE Report Form should be completed with study patient's details (e.g., patient number, initials, date of birth, investigational product information, etc.) and the details of the fetal SAE should be described in the narrative field of the SAE Report Form.

C. BRISTOL STOOL FORM SCALE

To be used for children in the 12 to < 18 age group.

Bristol Stool Chart

Type 1		Separate hard lumps, like nuts (hard to pass)
Type 2		Sausage-shaped but lumpy
Type 3		Like a sausage but with cracks on its surface
Type 4		Like a sausage or snake, smooth and soft
Type 5		Soft blobs with clear-cut edges (passed easily)
Type 6		Fluffy pieces with ragged edges, a mushy stool
Type 7		Watery, no solid pieces. Entirely Liquid

D. MODIFIED BRISTOL STOOL FORM SCALE FOR CHILDREN

[figure not shown]
To be used for children in the 6 to 11 age group.

The modified Bristol Stool Form Scale for Children (mBSFS-C)

1		Separate hard lumps, like nuts (hard to pass)
2		Sausage-shaped but lumpy

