3.2. RANDOMIZATION AND MASKING

This is a double-blind, placebo-controlled study with seven treatment age/dose groups that will be conducted at up to approximately 20 clinical sites. Subjects 6-11 years of age will be randomly assigned to 1 of 3 treatment groups (2 active treatments, 1 matching placebo) in a 1:1:1 ratio stratified by gender and subjects 12 to < 18 years of age will be randomly assigned to 1 of 4 treatment groups (3 active treatments, 1 matching placebo) in a 1:1:1:1 ratio stratified by gender using an Interactive Web-based Response System (IWRS).

Central, block randomization will be performed with stratification by gender.

Age Dose Group		Treatment		No. of Tablets to be Taken Daily	Dose Level	Number of Subjects
A	6 to 11 yrs. old	1	0.5 mg plecanatide	1	0.5 mg plecanatide	30
A	6 to 11 yrs. old	2	1.0 mg plecanatide	1	1.0 mg plecanatide	30

A	6 to 11 yrs. old	3	Matching placebo	1	placebo	30
B	12 to < 18 yrs. old	4	0.5 mg plecanatide	2	1.0 mg plecanatide	30
B	12 to < 18 yrs. old	5	1.0 mg plecanatide	2	2.0 mg plecanatide	30
B	12 to < 18 yrs. old	6	1.5 mg plecanatide	2	3.0 mg plecanatide	30
B	12 to < 18 yrs. old	7	Matching placebo	2	placebo	30

The study will be performed in a double-blind manner. All study drugs will be supplied in identical blister packs and tablets will be similar in color, smell, taste, and appearance, thereby assuring double-blind conditions.

The gender-stratified randomization schedule was prepared by Foehl Statistics & Analytics LLC.

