3.3. HANDLING OF DATA

3.3.1. Strata and Covariates

Enrollment will be stratified by age group (6 to 11 years and 12 to < 18 years). Randomization will be stratified by gender to ensure gender balance across treatment groups.

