5.2.4.4. Change from Baseline in Stool Consistency (mBSFS-C or BSFS)

Stool consistency for a bowel movement is measured using the mBSFS-C for subjects in Group A and the BSFS for subjects in Group B. The weekly average stool consistency scores will be determined using the approach defined in [Section 3.3.7](#) with missing scores excluded as described in [Section 3.3.4](#) and presented for each week in the 4-week treatment period. The change from baseline in the average weekly stool consistency score will be analyzed in the FAS Population using a linear mixed-effects ANCOVA model with fixed effects for gender (stratification variable), treatment, week, the interaction of treatment and week, and the corresponding baseline value; a random intercept for subject will also be specified. Least Squares (LS) means, with 95% confidence intervals and the corresponding statistical p-value, will be presented for each week, and across all 4 weeks, of the 4-week treatment period for the difference between the difference in LS means for each of treatment groups versus placebo, combined active doses within each age group versus placebo, and overall active doses versus placebo. The analysis of interest for this secondary endpoint is the difference in LS means between each plecanatide group and placebo for the estimated overall average change from baseline across the 4-week treatment period.

The baseline stool consistency (mBSFS-C or BSFS) rate will be calculated as the equally weighted average of the average stool consistency (mBSFS-C or BSFS) rate for each of the two weeks preceding initiation of study drug.

The above analysis will be repeated for the PP Population.

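### The SAP's overall plecanatide-versus-placebo models omit age group despite unequal allocation by age (a small bias), and the overall stool-consistency contrast pools a 5-point with a 7-point scale

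*Combined protocol and SAP*

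**What the plan says.** SAP 3.2 randomises within age group: children to two active doses or placebo at 1:1:1, adolescents to three active doses or placebo at 1:1:1:1, with 30 per arm. SAP 3.3.1 names age as a stratum: "Enrollment will be stratified by age group (6 to 11 years and 12 to < 18 years".

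SAP 5.2.2 analyses change in weekly SBM rate with a "linear mixed-effects model with fixed effects for gender (stratification variable), treatment, week, the interaction of treatment and week, and the corresponding baseline value", to which it adds a random intercept. Dose contrasts and combined-dose contrasts within an age group come from a separate model per age group. The pooled comparison is also requested: "and overall active doses versus placebo in a separate model with 95% confidence intervals and corresponding statistical p-values". Its covariates are those just listed, without age group. The rate endpoints in SAP 5.2.4.1, 5.2.4.2, 5.2.4.6, 5.2.4.7 and 5.2.4.8, and the pain and discomfort scores in 5.2.4.1 and 5.2.4.7, follow the same pattern.

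On stool consistency, SAP 5.2.4.4 says "Stool consistency for a bowel movement is measured using the mBSFS-C for subjects in Group A and the BSFS for subjects in Group B", and then plans LS mean differences for "combined active doses within each age group versus placebo, and overall active doses versus placebo". Protocol 8.8.2.4 planned only the "difference in LS means for each of treatment groups A and B versus Placebo". The protocol's other mixed-model endpoints all include a contrast for the two age groups combined; its stool section does not. SAP Section 7 does not list the added contrast as a change.

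**The concern.** There are two separate problems.

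**Age term.** The active-to-placebo ratio differs by age group, so pooled plecanatide and pooled placebo have different age mixes by design. Randomisation protects the comparison within an age group but not across them. Any age difference in change that gender and baseline do not absorb goes into the overall contrast, the only SBM contrast that uses all 210 patients.

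**Stool scale.** The two scales number the same stool differently. The form described as "Like a sausage or snake, smooth and soft" is type 4 in protocol Appendix C (BSFS) and type 3 in Appendix D (mBSFS-C). A pooled mean difference counts the same clinical improvement differently by age, and the result can be read on neither scale. The baseline covariate in a pooled model mixes the scales too.

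**Working it through.** **The plan's own figure.** SAP 3.1 states 81.5% power for 102 versus 34 patients, a difference of 1.5, and SDs of 3.5 (plecanatide) and 2.3 (placebo).

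- SE = sqrt(3.5²/102 + 2.3²/34) = 0.525.
- Power = Φ(1.5/0.525 - 1.96) = 81.5% at two-sided 0.05. This reproduces.
- The printed level of 0.05% would give 26.6%, so it is a typing slip.
- This calculation concerns Group B, whose contrast comes from its own model and is not affected below.

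**Bias of the overall SBM contrast.** Inputs from SAP 3.2: 60 active and 30 placebo children; 90 active and 30 placebo adolescents.

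- Share of children: plecanatide 60/150 = 0.40; placebo 30/60 = 0.50.
- Bias = (0.40 - 0.50) x d = -0.10 x d.

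The documents do not give d, so a range is shown:

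| d (SBM/week) | Error in overall contrast | Relative to 1.5 |
|---|---|---|
| 0 | 0 | 0% |
| +1 | 0.10 too low | 7% |
| -1 | 0.10 too high | 7% |
| ±2 | 0.20, sign opposite to d | 13% |

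The factor becomes 0.09 with 60 children and 150 adolescents, and 0.07 with 40 and 170. In a simulation of 10,000 null trials at the plan's SDs, the bias at |d| = 1 was 0.100 in size without an age term and 0.001 with it. The empirical SE was 0.412 without the term and 0.415 with it.

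**Type I error of the overall contrast.** The SAP describes no separate variances by arm, so the model SE uses one residual variance.

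- At the plan's SDs: residual variance = (149 x 3.5² + 59 x 2.3²)/208 = 10.28, plus 0.245 x d² for the unmodelled age spread. With sqrt(1/150 + 1/60) = 0.153, the model SE is 0.495 at |d| = 1 and 0.512 at |d| = 2.
- The true sampling SE is sqrt(3.5²/150 + 2.3²/60) = 0.412. The test is therefore conservative: 2.1% at |d| = 1 and 2.6% at |d| = 2.
- With a common SD between 2.3 and 3.5: 5.0-5.2% at |d| = 1 and 5.5-6.1% at |d| = 2.
- If the test used the unequal-variance SE of 0.412 instead: 5.7% and 7.7%.

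The consequence is mainly bias in the estimate; false positives rise little or not at all under the model as described.

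**Stool consistency.** A move from the lumpy sausage form (type 2 on both scales) to the smooth soft form scores +1 on the mBSFS-C and +2 on the BSFS. Let a fraction f of patients make this move without drug, and let the drug add a fraction g.

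- Effect in children: g points. Effect in adolescents: 2g points.
- Overall contrast as planned: 0.4(f+g) + 0.6 x 2(f+g) - (0.5f + 0.5 x 2f) = 1.6g + 0.1f.
- With an age term, the weights are 60 x 30/90 = 20 and 90 x 30/120 = 22.5, giving (20 + 2 x 22.5)/42.5 x g = 1.53g.
- With assumed f = 0.3 and g = 0.2: 0.20 in children, 0.40 in adolescents, 0.35 overall, and 0.31 overall with an age term.

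The age term removes the 0.1f contamination but still averages two units.

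**Related text.** SAP 3.3.7 puts patients expected to turn 12 before randomisation into Group B on the mBSFS, while SAP 5.2.4.4 assigns Group B the BSFS. If ages are spread evenly, that is 90/6 x 28/365 = 1.2 to 120/6 x 28/365 = 1.5 patients. One of them scoring +1 instead of +2 moves a 30-patient mean by 1/30 = 0.03. The stool tables in SAP 9.1 are split by age group, but every title names only the mBSFS-C.

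**The case against.** The age bias is minor. It depends on an unknown d, is 0.10 at |d| = 1, and does not touch the within-age SBM contrasts. The trial is declared exploratory. Protocol 8.8.1.1 omits age as well, and protocol Section 8 says the primary analysis will stay unchanged. All of this stands, and it is why a sensitivity analysis is an acceptable route. The appeal to an unchanged primary analysis is weaker than it looks: SAP 5.2.2 already adds a treatment-by-week interaction and moves to within-age placebo comparators, and Section 7 records neither.

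The stool issue is one contrast on one secondary endpoint. The SAP's statement of the analysis of interest there does not name the overall contrast explicitly, as it does for the pain scores. The protocol was not free of scale mixing either: it compared each age group with a placebo group pooled over both ages (protocol 8.4), and the SAP's within-age placebo reduces that. Under protocol Section 8 the SAP may also govern secondary analyses. These points limit the reach of the problem. They do not give the overall estimate a unit, and exploratory status does not either.

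Stratifying the overall log-rank and Wilcoxon tests would gain almost nothing. Simulated type I error under assumed age differences was 5.1-5.7% and 4.5-6.0% without stratification. Those changes are not needed.

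**Conclusion.** Both parts hold. The overall SBM contrast carries a bias of -0.10 x d at the planned allocation, 0.10 SBM per week at |d| = 1 and 0.20 at |d| = 2. Both values of d are assumptions. By itself this is minor, but it can be removed at almost no cost in precision. The overall stool-consistency contrast is wrong as written whatever the age effect; f and g only illustrate its size. The scale mismatch itself follows from the two appendices. Together the two parts should be corrected, although neither threatens the within-age SBM results or the Group B comparison behind the power statement.

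**What to change.** 1. Add age group as a fixed effect in every overall mixed model: SAP 5.2.2 and the rate and score models in 5.2.4.1, 5.2.4.2, 5.2.4.6, 5.2.4.7 and 5.2.4.8. This costs one degree of freedom per model plus text and programming. Because it changes the combined contrast of protocol 8.8.1.1, it needs a Section 7 entry and probably a protocol amendment under protocol 9.7. If the sponsor does not want to amend, keep the unadjusted contrast and prespecify the age-adjusted one as a sensitivity analysis.

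2. Delete the overall contrast from SAP 5.2.4.4, exempt stool consistency from the overall comparison listed in SAP Section 5, and report results by the scale used. This is a SAP text change only.

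3. State in SAP 5.2.4.4, and for the score analyses in 5.2.4.1 and 5.2.4.7, that within-age contrasts come from a separate model per age group, as 5.2.2 does.

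4. Reconcile SAP 3.3.7 with 5.2.4.4 on the scale used by patients turning 12, and correct the scale named in the Group B stool table titles. Both are editorial.

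5. Record in SAP Section 7 the within-age placebo comparator and the treatment-by-week interaction, since both depart from protocol 8.8.1.1.

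All of this should be settled before unblinding.

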5.2.3. Secondary Efficacy Endpoints

- Change from baseline in frequency and severity of abdominal pain and abdominal discomfort
- Change from baseline in frequency of BMs, SBMs, and CSBMs
- Time to First BM
- Change from baseline in stool consistency (BSFS or mBSFS-C)
- Use of Rescue Medication
- Change from baseline in frequency of fecal incontinence
- Change from baseline in frequency and severity of defecation pain
- Change from baseline in frequency of large diameter stools

